The study is a randomized controlled study where the participants will be randomized to an intervention consisting of preoperative physical exercise or a control group following standard preoperative care. The responsible researcher will perform the randomization. The assessors of physical performance will be blinded to group allocation during the study. This is made possible, as the randomization will be conducted after the baseline assessments. The participants will also receive written information not to reveal their group allocation at follow-up assessments. The intervention period will differ depending on individual variations in preoperative waiting time, but the intervention time will be a minimum of two weeks. To optimize compliance to and quality of the exercise, the intervention will be conducted by a physiotherapist in the participants' home. The results from the observational study will form the basis for possible stratification variables in the intervention study.

Intervention group

The participants will perform individually tailored functional strength training and aerobic training, as well as inspiratory muscle training starting from 30% of maximal inspiratory capacity. On none supervised days the participants will be encouraged to follow recommendations of 30 min physical activity on moderate intensity, and inspiratory muscle training at 20% of maximal capacity. The participants will also receive usual preoperative information.

Control group

The control group will receive usual preoperative information and be encouraged to follow recommendations of 30 min physical activity on moderate intensity at least 5 days/week. Both groups will receive usual postoperative treatment and rehabilitation.

Measurements

At baseline age, sex, comorbidities, smoking habits and living situation will be collected from the medical records. The following measurements will be conducted before the intervention, after the intervention but before surgery, and at discharge from the hospital:

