Six-minute walk, gait speed, chair stands, inspiratory muscle strength, lung function, and grip strength. Mortality, length of stay, discharge destination, postoperative complications (pneumonia, stroke, wound infections, pain etc), and comorbidities will be documented after 30 days and 90 days post surgery. Need of oxygen supplement and respiratory support, and saturation will be retained from the medical records. Data from medical records will be collected after approval from the head of the unit according to laws and regulations. Possible complications or adverse events related to testing or training will be documented.

At baseline and 6 month after surgery the participants will fill in three questionnaires (sent by mail) including activities in daily living (ADL-staircase), physical activity level (PASE), and health-related quality of life (EORTC QLQ-C30). All instrument are validated and frequently used in research both nationally and internationally. Reference values from the Swedish population are to be found for the EORTC QLQ-C30.

If the study results in positive findings with decreased length of stay and improved health-related quality of life, calculations regarding health economics will be performed where the costs of preoperative exercise are put in relations to decreased length of stay.

Statistical analyses

Continuous data will be described with mean and standard deviations, and ordinal data with median and interquartile range (q1-q3). Analyses between groups will be performed with intention-to-treat (ITT) analyses and with Repeated measure ANOVA for continuous normally distributed data and Wilcoxon/Kruskal-Wallis test for ordinal data and continuous skewed data. Analyses will be performed in SPSS.

2:5 Report whether collected biological material will be stored in a bio bank

NA

2:6 Documentation, data protection and archiving

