Karolinska Institutet, NVS, Division of Physiotherapy will be responsible for that the collected data will be de-identified, coded and stored in a safe way. The Division is also responsible for the code lists and only the PI will have access to these. During the study, at each recruiting site the patients' social security number and study code will be registered in a code key. On the questionnaires and documentation, only the study code will be documented. The participating sites are responsible to handle the collected data de-identified and according to instructions from the PI. After the data collection, material will be stored in a locked safe at Karolinska Institutet only available to the PI and co-applicants of the project. When collecting data from the Cause of death registry, instructions from The National Board of Health and Welfare will be followed.

2:7 Describe previous experiences (own and/or others) of the present procedure, technique or treatment

The PI and co-applicants have extensive experience of collecting data regarding physical activity and function, including pulmonary function. The methods used are well established nationally and internationally. Participating surgeons are responsible for selecting eligible patients so that exclusion criteria are followed and that data are collected without risk for the participants. The intervention could lead to complications such as muscle soreness and joint pain. Muscle soreness is a physiological response to strength training which leads to increased muscle strength. If the participants experience any inconvenience from joints associated with exercise programs or fatigue related to the disease, it will be modified. The randomization process means that half of the included people will not be offered the exercise intervention. Supervised preoperative exercise is not currently offered routinely before surgery and therefore this is considered to be of minor ethical significance. Physical exercise in frail elderly could pose a risk to the individual. However, studies in recent years have shown that this risk is small. The risks of physical inactivity are estimated to be equal or greater. Experiences from using the EORTC QLQ-30 questionnaire to collect data on patients' health-

related quality of life are positive. The questionnaire is easy to administer and for most people a time frame of less than 10 minutes is needed.

3. Information regarding research participants

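### RCT mortality is timed only from surgery and stated event capture is tied to testing or training, so deaths and serious events between randomisation and surgery cannot be compared fairly in an intention-to-treat analysis

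*Protocol*

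**What the plan says.** All of this is in Protocol section 2:4, Intervention study, unless noted.

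- **Randomisation:** "the randomization will be conducted after the baseline assessments".
- **Interval to surgery:** it varies with individual waiting time, but "the intervention time will be a minimum of two weeks". No upper limit is given.
- **Clock for the main clinical outcomes (Measurements):** the outcomes listed are "Mortality, length of stay, discharge destination, postoperative complications (pneumonia, stroke, wound infections, pain etc), and comorbidities". The same sentence then sets one clock for all of them: they "will be documented after 30 days and 90 days post surgery".
- **Physical function (Measurements):** measured "before the intervention, after the intervention but before surgery, and at discharge from the hospital".
- **Questionnaires (Measurements):** at baseline and six months after surgery.
- **Adverse events (Measurements):** "Possible complications or adverse events related to testing or training will be documented". Section 5:1 adds that the physiotherapist monitors exercise and possible adverse events at each supervised session.
- **Analysis (Statistical analyses):** "Analyses between groups will be performed with intention-to-treat (ITT) analyses".
- **Role of mortality:** the summary in 2:1 lists it among the effects to be studied, with no restriction to the period after surgery. The research question in 2:2 does not name it.
- **Source for deaths:** the Cause of death registry is named in 2:4 for the observational study and again in 2:6, which covers the whole project.

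**The concern.** The intervention is delivered entirely between randomisation and surgery, but the mortality clock starts at surgery. For a patient who never reaches surgery, days 30 and 90 after surgery do not exist. If the text is followed as written, nothing fixes whether or when that patient's death enters the mortality comparison.

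Event recording has a related weakness. It is defined by relation to testing or training. Both arms are tested, but only one arm trains and has supervised sessions. A serious preoperative event judged unrelated has no stated capture in either arm. A training-related event can be recorded in one arm only.

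This matters because section 2:7 acknowledges that "Physical exercise in frail elderly could pose a risk to the individual", and the trial is aimed at older people at high risk. Any harm, or any benefit, of exercise before surgery would fall in the period that the mortality time points do not cover.

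**Working it through.** **1. Time points for each kind of patient, as the text stands**

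| Randomised patient | Mortality at 30 and 90 days | Serious event before surgery |
|---|---|---|
| Operated on | Defined | Recorded if related to testing or training |
| Alive, never operated on | Undefined (no surgery date) | Same rule |
| Dies before surgery | Undefined (no surgery date) | Same rule |

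Intention-to-treat concerns all three rows. The stated mortality time points exist only for the first.

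**2. The protocol's own figure**

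Section 3:3 quotes 584 patients (292 per group) from a previous study. It is not this trial's sample size, which is still to be calculated, and the complication rate behind it is not given. Assuming a fall from 30% to 20%, two-sided 5% and 80% power, the unpooled formula gives

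n = (1.96 + 0.84)² × (0.30 × 0.70 + 0.20 × 0.80) / 0.10² ≈ 290.4, so 291 per arm.

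The pooled formula gives 294. The quoted figure is plausible. The point does not rest on it; 292 serves below only as a scale.

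**3. What a surgery clock can miss for mortality (all rates assumed)**

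Let *a* be the risk of death before surgery and *m* the 90-day mortality after surgery, with *m* equal in both arms and every survivor operated on. Mortality from randomisation is a + (1 − a)m. The difference between arms (E exercise, C control) is then

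(a_E − a_C)(1 − m),

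whereas a count limited to patients with a surgery date shows a difference of zero. With m assumed at 3% to 5%:

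| a_C vs a_E | Difference not seen (percentage points) | Deaths per 292 |
|---|---|---|
| 1% vs 1% | 0 | 0 |
| 0.5% vs 1% | 0.475 to 0.485 | about 1.4 |
| 1% vs 2% | 0.95 to 0.97 | about 2.8 |
| 0.5% vs 2% | 1.425 to 1.455 | about 4.2 |

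If exercise lowered preoperative deaths, the sign would reverse.

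**4. Why non-operation should be reported by arm (all rates assumed)**

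Take an outcome with 30% risk overall, 60% in patients never operated on, and no true effect. If a share *d* is not operated on, the risk among operated patients is (0.30 − 0.60d)/(1 − d):

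- d = 2%: 0.288/0.98 = 29.4%
- d = 5%: 0.27/0.95 = 28.4%
- d = 10%: 0.24/0.90 = 26.7%
- d = 15%: 0.21/0.85 = 24.7%

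Equal loss gives no difference. Control versus exercise at 2% vs 5%, 5% vs 10% and 5% vs 15% gives spurious reductions of 1.0, 1.8 and 3.7 points in an operated-only comparison. The protocol does not prescribe that comparison. The sums show only that any distortion depends on loss differing between arms.

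**The case against.** The strongest reply is that the protocol states when outcomes are documented, not who is excluded. A reader might infer that deaths before surgery are ignored and that patients never operated on drop out of the analysis. The document supports neither: no section says so, the text commits to intention-to-treat, and the handling of such patients could sit in a statistical analysis plan that is not at hand. That part of the reply stands, and the absence of a handling rule is not the point made here.

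Second, a reader might think that every outcome is wrongly timed. That is also not so. Postoperative complications, length of stay and discharge destination presuppose an operation, and surgery is their proper origin. Only mortality has a real timing problem.

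Third, the exercise period is not unobserved. Function is measured again before surgery, testing-related events can arise in both arms, and comorbidities are documented again at 30 and 90 days. These are true, but none of them provides a count of deaths or serious events that is collected alike in both arms from randomisation.

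Fourth, the document gives no rate of preoperative death or cancelled surgery, and no evidence that either would differ between arms. This stands, and it limits what can be said about size.

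What the reply does not remove is the effect of two rules that are stated: a mortality clock that starts at surgery, and event recording limited by relatedness. Analysis rules written later cannot supply serious events that were not collected.

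**Conclusion.** The concern holds for mortality and for serious events before surgery. Randomisation precedes at least two weeks of exercise, mortality is given time points only after surgery, stated event capture depends on relation to testing or training, and the analysis is called intention-to-treat. Followed as written, this leaves some randomised patients without a defined mortality time point and makes the preoperative safety comparison uneven between arms.

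The size cannot be derived from the document. Every rate in the illustrations is an assumption, and 292 per group belongs to a previous study. Bias between arms requires loss or death before surgery to differ between them; with equal loss the illustrations show none. The change should be made because it is cheap and because the uncovered interval is the one in which the intervention is given.

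**What to change.** 1. **Mortality:** add all-cause mortality from randomisation to a fixed time in all randomised patients, alongside the 30- and 90-day post-surgery time points. Use the Cause of death registry already named in 2:4 and 2:6. The fixed time should be long enough to cover the expected wait plus 90 days after surgery.
2. **Serious adverse events:** record them from randomisation in both arms, whatever the judged cause, from the medical records. Keep the existing record of testing- and training-related events as an additional item.
3. **Patients not operated on:** report number and reasons by arm. Keep these patients in the intention-to-treat analysis of mortality and of outcomes that do not require an operation. Leave postoperative complications, length of stay and discharge destination timed from surgery.

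The cost is a change of wording in the protocol and case forms and slightly more data collection, from sources already in use. No treatment rule changes.

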The risk with physical activity/exercise is not considered higher than the risks of undergoing surgery. Resistance exercise might lead to muscle soreness, however the participant will be informed that muscle sourness related to exercise is an indication of increased muscle activity which in turn is a requirement for increased muscle strength. The exercise and possible adverse events are monitored by the physiotherapist at each supervised session and modified

if needed. The questions regarding quality of life (EORTC QLQ-C30) are used in multiple studies, both in Sweden and internationally. It has also been tested if they are perceived as worrying or offensive, which was not the case.

5:2 Describe the possible benefits for the research persons included in the project

The participants of the study will get an opportunity to a structured assessment of their physical status and function, which is not a part of the standard care and can therefore be considered an advantage giving the participants a full picture of their physical health. Participants randomized to the exercise group will also be given the opportunity to improve their physical function, which can be of importance for their daily activities and postoperative recovery.

5:3 Identify possible ethical problems that might appear from the project

If positive results of the overall project can be shown, the knowledge can benefit older people in general undergoing abdominal- or thoracic surgery. Ethical problems appearing in form of risk in a further perspective is not considered to exist. Even if no positive exercise effects can be shown from the study, the pros of being physically active in general is considered positive in relation to other health factors.

6. Reporting of the results

6:1 How is the principal investigator and participating researchers guaranteed access to data and who is responsible for data processing and report writing?

Only the PI and co-researchers stated in this application will have full access to data. Apart from doctoral students and postdocs involved in the studies, coworkers at participating clinics will be able to assess some data in relation to master thesis and thesis by resident physicians that are under supervision from PI and/or co-applicants of this project.

6:2 How will the results be made publicly available? Will the study be submitted for publication in a journal or be published in any other way?

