As new findings indicate that the training should be of high-intensity but with shorter intervals, the participants will now train at 50-70% of their maximum capacity and perform 30 breaths x2 at this level. The training will take place daily, but under the supervision of the physiotherapist 2-3 days/w.

b) *"Individually adapted functional training.... This will be combined with functional exercises related to each individual's needs, such as to carry and move things."*

In addition the participants will, together with the physiotherapist, complete the form "Patient-specific function scale" where the participant can describe three important activities that they have problems performing or cannot perform at all. They then will estimate how difficult they think it is to perform the activity on a scale from 0=cannot perform the activity to 10=can perform the activity without any problem. These activities will be incorporated in the training program and followed up after the intervention. See Appendix 1 for updated patient information.

3.

Purpose

To evaluate whether a combination of pre-operative physical activity and an intensified nutritional treatment prior to abdominal surgery increases appetite and nutritional intake and thus prevents the reduction of muscle mass and physical function in older patients at risk of malnutrition.

Overview of topic

The number of frail older people is increasing in line with an aging population. Protein requirements increase with increasing age, while disease and treatment can lead to several inhibiting factors for appetite and nutritional intake. Malnutrition can therefore be a problem

before and after treatment has been completed. Loss of muscle mass and function can be directly harmful and can be associated with poorer prognosis. Strength training can improve muscle function and balance in frail older people, but on the other hand can put a patient in a catabolic state unless energy and protein are supplied in sufficient amount. Computer tomography, CT is generally used to identify the presence of tumor but not in the evaluation of malnutrition.

Method

Design; Intervention study

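### Before surgery, adverse events are documented only if related to testing or training, and no enquiry common to both arms is described, so preoperative counts cannot be compared fairly

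*Protocol*

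**What the plan says.** Four places in the protocol bear on this.

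- **Section 2:4, Intervention study, Measurements** gives the documentation rule: "Possible complications or adverse events related to testing or training will be documented". It does not say who judges relatedness, by what criteria, or when events are sought.
- **Section 5:1** gives the only description of how such events come to light: "The exercise and possible adverse events are monitored by the physiotherapist at each supervised session". Sessions belong to the exercise arm.
- **Amendment, part 2 a)** changes the inspiratory muscle training: "The training will take place daily, but under the supervision of the physiotherapist 2-3 days/w". Section 2:4 adds that "the intervention time will be a minimum of two weeks".
- **Section 2:4** asks for activity outside sessions in both arms. For the exercise arm: "On none supervised days the participants will be encouraged to follow recommendations of 30 min physical activity on moderate intensity". Controls are "encouraged to follow recommendations of 30 min physical activity on moderate intensity at least 5 days/week".

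The same Measurements text also has mortality, complications after surgery and comorbidities documented at 30 and 90 days. That part has no relatedness condition and is not limited to one arm.

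**The concern.** The difficulty concerns the weeks between randomisation and surgery. Attribution decides whether an event is written down at all, and the described opportunity to notice one exists in one arm only. A control who falls, develops joint pain or becomes fatigued while waiting has no trial training to which the event could be related, and is not described as being asked. An exercise participant with the same event is seen several times and may have it recorded.

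An apparent excess in the exercise arm could then come from contact and attribution alone, and a true excess could be dismissed for the same reason. Sections 2:7 and 5:1 tell the ethics board that exercise carries little risk in frail older people and that inactivity carries at least as much. Readers will look to this trial's own harms data for reassurance on that, and preoperative counts collected this way could not give it. The defect lies in collection, so a statistical analysis plan cannot repair it.

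**Working it through.** The protocol states no harms figure, so there is none to reproduce. The check consists of counts and one illustration.

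**1. Unsupervised training days (inspiratory training as amended).** Inputs: daily training and *s* = 2 or 3 supervised days per week (Amendment, part 2 a); minimum 14 days (section 2:4).

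- Share unsupervised = (7 − *s*)/7: 5/7 = 71% for *s* = 2; 4/7 = 57% for *s* = 3.
- Over 14 days = 14 − 2*s*: 10 days for *s* = 2; 8 days for *s* = 3.

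No supervised frequency is given for the strength and aerobic training, so these shares cannot be extended to it.

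**2. Trial contacts after randomisation and before surgery, over 14 days.** Inputs: the sessions above, plus the one test visit before surgery, which section 2:4 does not restrict to one arm.

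- Exercise arm = 2*s* + 1: 5 for *s* = 2; 7 for *s* = 3.
- Control arm: 1.

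**3. Illustration of what unequal contact can do.** Assumptions, none from the protocol: the same true event rate in both arms; each contact after an event elicits it independently with probability *q*, from 0.2 to 0.5; the relatedness condition is set aside. For an event early enough to be open to all contacts, the chance of detection is 1 − (1 − *q*)^contacts.

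| *q* | Exercise, 5 contacts | Exercise, 7 contacts | Control, 1 contact | Ratio |
|---|---|---|---|---|
| 0.2 | 1 − 0.8^5 = 0.67 | 1 − 0.8^7 = 0.79 | 0.20 | 3.4 to 4.0 |
| 0.5 | 1 − 0.5^5 = 0.97 | 1 − 0.5^7 = 0.99 | 0.50 | 1.9 to 2.0 |

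For an event just before the last session, only two contacts remain in the exercise arm. The ratio is then (1 − 0.8²)/0.2 = 1.8 or (1 − 0.5²)/0.5 = 1.5. For an event after the last session it is 1. The range 1.9 to 4.0 is thus the upper end, for early events.

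**4. The relatedness condition.** As written, events related to testing can be recorded in both arms and events related to training only in the exercise arm. Section 2:7 shows that relatedness is a real judgement: it foresees modifying the programme for fatigue caused by the disease. Such fatigue could change the training and yet fall outside the documentation rule.

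**5. Other preoperative routes.** Part 3 of the amendment gives patients at risk of malnutrition, in both arms, weekly telephone support until surgery. It covers that subset only and states no question about harms. The 30- and 90-day records concern the period after surgery and describe no enquiry about falls, pain or fatigue before it.

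**The case against.** The strongest reply is that the protocol announces no between-arm comparison of preoperative adverse events. Events tied to testing or training may be meant only as a description of tolerability, and the claim of small risk rests on previous studies, not on a hypothesis of this trial. That stands, and it limits the stakes: no stated analysis is invalidated. It does not remove the point, because counts gathered in a randomised trial are readily compared by arm.

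Several stronger readings are tempting, and the documents do not support them.

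- *All harms are filtered by relatedness, and controls are hardly observed.* A reader might infer this from the documentation rule alone. The same section documents mortality and postoperative complications at 30 and 90 days without that filter and without restriction by arm.
- *No control event before surgery can be recorded.* Controls are tested too, so test-related events can be. What lacks a stated route is everything else.
- *Events are sought only at sessions, and the treating physiotherapist decides attribution.* Section 5:1 says monitoring happens at each supervised session, not that it happens nowhere else, and no text says who judges relatedness. An event on an unsupervised day might be reported at the next visit; nothing requires or prevents this.
- *Most of all training is unmonitored.* The 57-71% applies to the amended inspiratory training only.
- *The artificial excess can be given a definite size.* It cannot. Assuming high detection of background events in the exercise arm would also contradict the relatedness condition, which should discard many of them there.

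**Conclusion.** The point holds for adverse events between randomisation and surgery. The rule keeps only events related to testing or training, the only monitoring described takes place at sessions that controls do not have, and no enquiry common to both arms or covering unsupervised days is described. Preoperative counts therefore cannot be compared fairly between arms.

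The firm figures are 4-5 unsupervised days of 7 for the amended inspiratory training, and 5-7 contacts against 1 over the two-week minimum. The 1.9- to 4.0-fold ratio is an illustration under assumed detection probabilities, not an estimate. The conclusion assumes that sites follow the protocol as written and that the encouraged activity of controls does not count as training under the rule. Mortality and postoperative complications at 30 and 90 days are untouched. This should be corrected, but it does not threaten the trial's main comparisons.

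**What to change.** In section 2:4, Measurements, replace the rule with one that records all adverse events from randomisation to surgery in both arms regardless of attribution, with relatedness as a separate field.

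- Collect them with one short self-completed form, identical in both arms and neutral about exercise, at the pre-surgery assessment already planned.
- Have the form returned sealed or by mail, so that the blinded assessor does not see it. The trial already uses mailed questionnaires at 6 months.
- At each supervised session, also ask about events since the previous session, so that unsupervised days are covered.
- Use only the common form for any between-arm comparison. Report session-found events descriptively for the exercise arm.

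The cost is a one-page form at an existing visit, some handling to protect the blinding, and a change of wording. The downsides are small: more minor, unrelated events will be recorded, and recall spans a few weeks.
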